### **10.8 Regulatory Aspects of Adverse Event Reporting**

All SAEs, regardless of relationship to study drug, must be reported to the sponsor or designee within 24 hours of knowledge of the event, according to the procedures below. It is important

that the investigator provide an assessment of relationship of the SAE to study treatment at the time of the initial report. The Clinical Trial Serious Adverse Event Report Form must be used for reporting SAEs.

The sponsor or its designee is responsible for submitting reports of AEs associated with the use of the drug that are both serious and unexpected to the U.S. Food and Drug Administration (FDA), according to 21 Code of Federal Regulations (CFR) 312.32; to the Japanese Pharmaceuticals and Medical Devices Agency (PMDA); to the European regulatory authorities according to the European Commission Clinical Trials Directive (2001/20/EC); and to other regulatory authorities, according to national law and/or local regulations. All investigators participating in ongoing clinical studies with the study medication will receive copies of these reports for prompt submission to their Institutional Review Board (IRB) or Independent Ethics Committee (IEC). In accordance with the European Commission Clinical Trials Directive (2001/20/EC), the sponsor or its designee will notify the relevant ethics committees in concerned member states of applicable suspected unexpected serious adverse reactions (SUSARs) as individual notifications or through periodic line listings.

The sponsor or its designee will submit all safety updates and periodic reports to the regulatory authorities as required by applicable regulatory requirements.

## 11 STATISTICAL METHODS

### 11.1 Populations

The following analysis populations are defined for the study:

**PK-evaluable Population**—all patients who received at least one dose of CO-1686 and have adequate PK assessments drawn for determination of the PK profile. Adequacy will be determined on a case-by-case basis and will be assessed prior to analysis of the blood samples.

**Food-effect PK Population**—all patients who enrolled into a food-effect PK evaluation cohort who received CO-1686 on both Day -7 and Day 1, complied with the fed and fasted requirements, and have sufficient PK data for a comparison to be made between the fasted and fed state.

**ECG/PK Comparison-Evaluable Population**—all patients in Phase 1 and Phase 2 who have received CO-1686 and have had adequate PK and ECG assessments performed for determination of the ECG effects and the relationship between PK and ECG.

**Safety Population**— all patients who have received at least one dose of CO-1686.

**DLT-evaluable Population**—all patients enrolled into Phase 1 of the study who received at least 80% of scheduled doses of CO-1686 and completed Cycle 1 of treatment, or who experienced a DLT in Cycle 1.

**Tumor-evaluable Population**—all patients who received at least one dose of CO-1686, have measurable tumor lesions at baseline, and have at least one post-baseline disease assessment.

### 11.2 Statistical Methods

#### 11.2.1 General Considerations

Quantitative variables will be summarized using descriptive statistics (N, mean, standard deviation, median, minimum, and maximum) and/or frequency and percentages for medically relevant categories. Categorical variables will be presented using frequencies and percentages. The Kaplan-Meier methodology will be used to summarize time-to-event variables. If estimable, the 25th, 50th (median), and 75th percentiles will be presented. The number of patients with events and the number of censored patients will also be presented.

Individual patient data listings will be provided to support summary tables. All data will be used to their maximum possible extent but without any imputations for missing data.

All statistical analyses will be conducted with the statistical analysis software (SAS®) System, Version 9.1 or higher.

#### 11.2.2 Patient Disposition

Separately for Phase 1 and Phase 2 of the study, the frequency and percentage of patients in each analysis population will be presented. The primary reason for discontinuation of CO-1686 will be summarized.

### **11.2.3 Baseline Characteristics**

Separately for Phase 1 and Phase 2 of the study, baseline characteristics and demographic data will be summarized for the safety population.

### **11.2.4 Efficacy Analyses**

#### **11.2.4.1 Phase 1**

##### **Overall Response Rate - Secondary Endpoint**

A secondary endpoint in Phase 1 of the study (overall response rate) is the best overall response recorded from the start of the treatment until disease progression or recurrence. The overall response rate will be summarized for the tumor-evaluable population enrolled in Phase 1 with frequencies and percentages.

For patients who continue treatment post-progression, the first date of progression will be used for the analysis.

##### **Duration of Response - Secondary Endpoint**

Duration of response for complete response (CR) and partial response (PR) will be measured from the date that any of these best responses is first recorded until the first date that progressive disease is objectively documented. Duration of response will be summarized using descriptive statistics (N, mean, standard deviation, median, minimum, and maximum) as well as categorically.

#### **11.2.4.2 Phase 2 (Cohorts A to C)**

The efficacy results from Phase 1 and Phase 2 may be presented together for certain dose groups of interest.

##### **Objective Response Rate (ORR) - Primary Endpoint**

A primary endpoint in Phase 2 of the study (objective response rate) is the best response recorded from the start of the treatment until disease progression or recurrence. The frequency and percentages of patients with a best response of CR, PR, stable disease (SD), or progressive disease (PD) will be summarized for the tumor-evaluable and safety populations enrolled in Phase 2. The response rate (CR+PR) will also be presented with frequencies and percentages.

For patients who continue treatment post-progression, the first date of progression will be used for the analysis.

The ORR will be evaluated by the investigator with the primary analysis based on investigator assessment.

##### **Duration of Response - Primary Endpoint**

Duration of response for CR and PR will be measured from the date that any of these best responses is first recorded until the first date that PD is objectively documented. Duration of response will be summarized using descriptive statistics (N, mean, standard deviation, median, minimum, and maximum) as well as categorically.

The duration of response will be evaluated by the investigator with the primary analysis based on investigator assessment.

## **Objective Response Rate (ORR) by IRR- Secondary Endpoint**

A secondary endpoint in Phase 2 of the study (objective response rate) is the best response recorded from the start of the treatment until disease progression or recurrence. The frequency and percentages of patients with a best response of CR, PR, SD, or PD will be summarized for the tumor-evaluable and safety populations enrolled in Phase 2. The response rate (CR+PR) will also be presented with frequencies and percentages.

For patients who continue treatment post-progression, the first date of progression will be used for the analysis.

The ORR will be evaluated by the central independent radiology review (IRR).

## **Duration of Response by IRR – Secondary Endpoint**

Duration of response for CR and PR will be measured from the date that any of these best responses is first recorded until the first date that PD is objectively documented. Duration of response will be summarized using descriptive statistics (N, mean, standard deviation, median, minimum, and maximum) as well as categorically.

The duration of response will be evaluated by the IRR with the analysis based on independent assessment.

## **Overall Survival (OS) - Secondary Endpoint**

Overall survival (OS) will be calculated as 1+ the number of days from the first dose of study drug to death due to any cause. Patients without a documented date of death will be censored on the date the patient was last known to be alive.

## **Disease Control Rate (DCR) - Secondary Endpoint**

The DCR is the percentage of patients with a best response of CR, PR, or SD for at least 12 weeks.

The DCR will be evaluated by the investigator and the IRR.

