#### **5.1.3 Phase 2**

This phase of the study will consist of a screening phase to establish study eligibility and document baseline measurements, an open-label treatment phase, in which patients will receive CO-1686 to ascertain safety and efficacy until protocol-defined disease progression. Each 21-day period of treatment will represent one cycle, with dosing initiated on Cycle 1 Day 1. Eligible patients are those who are confirmed by the sponsor's central laboratory (Cohorts A and B) or by local assessment (Cohort C) to have the T790M mutation in FFPE tumor tissue.

The assessments for patients in each Phase 2 cohort will be identical.

Enrollment into Part 2 was initiated in February 2014 under Amendment 4 when a RP2D of 750 mg BID was selected. This initial RP2D of 750 mg BID was selected based on early Phase 1 efficacy data and two expansion cohorts (Cohorts A and B) are currently enrolling at this dose. As the Phase 1 efficacy data matured, the recommended dose was adjusted to 625 mg BID, and under this amendment patients will no longer enroll in the 750 mg BID dose level for Cohorts A and B, but will be assigned by the sponsor to receive either 625 mg BID or 500 mg BID in these cohorts. Patients who are already receiving 750 mg BID will continue at this dose. Cohort A comprises later-line patients who have previously received one or more prior EGFR TKI, and irrespective of the number and order of previous lines of NSCLC therapy, and who are not eligible for Cohort B. Cohort B comprises earlier-line patients who have had radiologic progression on one prior single agent EGFR TKI for advanced/metastatic NSCLC, and have had

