### **9.8.2 Efficacy Evaluations**

#### 9.8.2.1 Tumor Assessments

Tumor assessments will be performed at screening; at the end of Cycles 2, 4, and 6 (between Days 14 and 21); every 3 cycles after Cycle 6 (between Days 14 and 21); and at the End of Treatment visit. Tumor response will be interpreted using RECIST Version 1.1 ([Appendix A](#)).

If an initial CR or PR is noted at Cycle 7 or beyond, confirmatory scans must be performed 4 to 6 weeks later. In the case of SD, follow-up measurements must have met the SD criteria at least once after study entry at a minimum interval of no less than 6 to 8 weeks.

Patients who continue treatment with CO-1686 post-progression should continue to be scanned according to the protocol until they discontinue from the study.

Tumor assessments should consist of clinical examination and appropriate imaging techniques (preferably CT scans of the chest, abdomen, and pelvis with appropriate slice thickness per RECIST Version 1.1); other studies (MRI and X-ray) may be performed if required. The same methods used to detect lesions at baseline are to be used to follow the same lesions throughout the clinical study.

Brain imaging (MRI/CT) is required at baseline. Patients with known brain metastases and/or brain lesions detected at baseline are required to repeat brain imaging as part of the follow-up tumor assessments. The same methods used to detect brain lesions at baseline are to be used to follow the same lesions throughout the clinical study.

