### Time Point Response

A response assessment will occur at the protocol-specified time points. The tables below provide a summary of the overall response status calculation at each time point for patients who have measureable and non-measureable disease (non-target disease only).

Time Point Response: Patients with Target (+/- non-target) Disease			
Target Lesions	Nontarget Lesions	New Lesions	Overall Response
CR	CR	No	CR
CR	Non-CR/non-PD	No	PR
CR	Not evaluated	No	PR
PR	Non-PD or not evaluated	No	PR
SD	Non-PD or not evaluated	No	SD
Not Evaluated	Non-PD	No	NE
PD	Any	Yes or No	PD
Any	PD	Yes or No	PD
Any	Any	Yes	PD

NE=Not evaluable.

Evaluation of Best Overall Response When Confirmation of CR and PR Required		
Overall Response First Time Point	Overall Response Subsequent Time Point	Best Overall Response
CR	CR	CR
CR	PR	SD, PD or PR a
CR	SD	SD provided minimum criteria for SD duration met, otherwise, PD
CR	PD	SD provided minimum criteria for SD duration met, otherwise, PD
CR	NE	SD provided minimum criteria for SD duration met, otherwise, NE
PR	CR	PR
PR	PR	PR
PR	SD	SD
PR	PD	SD provided minimum criteria for SD duration met, otherwise, PD
PR	NE	SD provided minimum criteria for SD duration met, otherwise, NE
NE	NE	NE

a If a CR is truly met at first time point, then any disease seen at a subsequent time point, even disease meeting PR criteria relative to baseline, makes this disease PD at that point (since disease must have reappeared after CR). Best response would depend on whether minimum duration for SD was met. However sometimes 'CR' may be claimed when subsequent scans suggest small lesions were likely still present and in fact the patient had PR, not CR at the first time point. Under these circumstances, the original CR should be changed to PR and the best response is PR.

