### **Confirmatory Measurement/Duration of Response**

#### Confirmation

CT scans are required within 7 days prior to the start of Cycles 3, 5, and 7, and then within 7 days prior to the start of every third cycle of treatment thereafter, beginning with Cycle 10. If an initial CR or PR is noted at Cycle 7 or beyond, confirmatory scans must be performed 4 to 6 weeks later. In the case of SD, follow-up measurements must have met the SD criteria at least once after study entry at a minimum interval of no less than 6 to 8 weeks.

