#### Duration of Stable Disease

SD is measured from the start of the treatment until the criteria for progression are met, taking as reference the smallest measurements recorded since the treatment started.

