### **2.3.1 Schedule of Assessments**

The procedures and assessments to be performed during the study are outlined in the Schedule of Evaluations in the protocol.

Patients in the Phase 2 portion of this study will receive CO-1686 at 500 mg BID, 625 mg BID or 750 mg BID. Treatment will continue until disease progression, patient withdraws consent for further treatment, or by investigator decision. Treatment can continue post-progression if, in the opinion of the investigator and approved by the sponsor, the patient has indolent progression with evidence of continued clinical benefit from treatment. The study consists of screening, treatment, and follow-up periods.

Within 28 days prior to Cycle 1 Day 1, patients will be screened and evaluated for eligibility for the study. During the treatment period, patients will return to the clinic for study drug and to be evaluated for safety and dosing compliance. Each cycle consists of 21 days. Imaging will be done at the end of Cycles 2, 4, and 6 (between Days 14 and 21) and every 3 cycles after Cycle 6 (between Days 14 and 21).

During the follow-up period, patients will be followed for survival, related serious adverse events (SAEs) and next therapy for NSCLC every 2 months until lost to follow-up, withdrawal of informed consent or sponsor decision. The follow-up data may be collected by visit, telephone or chart review.

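### The stable-disease minimum and the 12-week disease-control threshold sit at or beyond the end of the scan windows, with no allowance and two conflicting rules for SD

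*Protocol*

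**What the plan says.** **Timing.** Protocol 5.1.3: "Each 21-day period of treatment will represent one cycle, with dosing initiated on Cycle 1 Day 1". Protocol 9.8.2.1 places scans "at the end of Cycles 2, 4, and 6 (between Days 14 and 21", then every three cycles. SAP 2.3.1 agrees: "Imaging will be done at the end of Cycles 2, 4, and 6 (between Days 14 and 21". Appendix A (Confirmation) words it as "CT scans are required within 7 days prior to the start of Cycles 3, 5, and 7".

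**SD minimum.** For stable disease, Appendix A (Confirmation) sets this condition on later scans: "must have met the SD criteria at least once after study entry at a minimum interval of no less than 6 to 8 weeks". Protocol 9.8.2.1, the Synopsis and the footnotes to Tables 10 and 11 say the same. Neither document chooses between 6 and 8 weeks or defines study entry.

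**SD duration.** Appendix A (Duration of Stable Disease): "SD is measured from the start of the treatment until the criteria for progression are met".

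**Consequence of missing the minimum.** In Appendix A's best-overall-response table, a PR followed by PD becomes "SD provided minimum criteria for SD duration met, otherwise, PD".

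**DCR.** Protocol 11.2.4.2: "The DCR is the percentage of patients with a best response of CR, PR, or SD for at least 12 weeks". It is to be evaluated by investigator and by IRR. SAP 10.2 lists DCR on both bases, but SAP section 11 contains no definition or analysis of it, and SAP section 15 does not list it among the analyses dropped.

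**The concern.** Cut-offs for best response are normally placed so that any on-time scan can satisfy them. Here both cut-offs sit at the far edge of the window or past it, and no tolerance is given. A patient scanned correctly but early in the window can then miss a threshold that an identical patient scanned a few days later meets.

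Separately, one rule asks for an SD measurement at the minimum interval, while another lets SD run until progression. Two programmers following the text could produce different SD, PD and DCR counts. SAP section 1 says these analyses are for the NDA and MAA, and DCR is a named secondary variable there.

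**Working it through.** The plan gives no expected value, power or precision for SD or DCR, so there is no planning figure to reproduce. The check is day arithmetic.

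**1. Scan windows.** Study day = 21 × (cycle − 1) + day of cycle.
- Cycle 2: 21 + 14 = 35 to 21 + 21 = 42.
- Cycle 4: 63 + 14 = 77 to 63 + 21 = 84.
- Cycle 6: 105 + 14 = 119 to 105 + 21 = 126.

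Appendix A's wording (the seven days before Cycles 3, 5 and 7, whose Day 1s are Days 43, 85 and 127) gives Days 36-42, 78-84 and 120-126, the same to within one day.

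**2. Thresholds against the eight days of each window.** The +1 count is stated for OS and PFS (Protocol 11.2.4.2) but not for SD, so both counts are shown.

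| Threshold | Scan | Days qualifying, +1 count | Days qualifying, elapsed |
|---|---|---|---|
| 6 weeks = 42 days | Cycle 2 | 1 of 8 | 0 of 8 |
| 8 weeks = 56 days | Cycle 2 | 0 of 8 | 0 of 8 |
| 12 weeks = 84 days | Cycle 4 | 1 of 8 | 0 of 8 |

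Every Cycle 4 scan passes both SD minimums, and every Cycle 6 scan passes 12 weeks.

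**3. A different start date.** Table 11 allows baseline scans up to 28 days before Day 1. If study entry meant the baseline scan, the first on-study scan would come 35 − 1 = 34 to 42 − 1 + 28 = 69 days later, and the Cycle 4 scan 76 to 111 days later. The thresholds would then fall inside the windows, so the undefined start date changes the answer.

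**4. One patient, two rules.** SD on Day 38, PD on Day 80.
- Measurement rule: the only SD measurement is at 38 days, short of 42. The minimum is not met and best response is PD.
- Run-to-progression rule: SD lasts 80 days, past both 42 and 56. Best response is SD.

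An unconfirmed PR on Day 38 followed by PD on Day 80 meets the same fork through an explicit row of Appendix A's table. That table has no SD-first row, so for the SD patient the relabelling is an extension of its rule.

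**5. DCR at Cycle 4.** Under run-to-progression with the +1 count, PD first seen on Day 84 gives 84 days and counts as disease control; PD first seen on Days 77-83 does not. If instead a non-progressing scan at 84 days or later is required, a patient with SD on Day 80 and PD at Cycle 6 is not counted, although the run-to-progression rule counts that patient.

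**6. Steepness of the one-day step (illustration on assumed medians).** Take non-responders with exponential time to progression, median m, all scanned on the same window day, under run-to-progression. With the Cycle 4 scan on Day 83, the proportion counted is 0.5^(83/m). With scans on Days 42 and 84, it is 0.5^(42/m).
- m = 90: 0.528 against 0.724.
- m = 120: 0.619 against 0.785.
- m = 240: 0.787 against 0.886.

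This is the most extreme contrast; real scans would be spread over the window.

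**7. How much of DCR rests on SD.** The only DCR in the documents is Protocol Table 5 (Phase 1): 20/22 = 90.9%, made up of 14 PR (63.6%) and 6 SD (6/22 = 27.3 points), on a row showing no 12-week condition.

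**The case against.** - **The End of Treatment scan.** Protocol 9.6 and 9.8.2.1 require a scan 28 ± 7 days after the last dose unless progression was documented or the last scan was under two weeks before. A patient still dosing at a Day 77 scan who then stops is rescanned no earlier than 77 + 21 = Day 98; one who stops at a Day 35 scan, no earlier than Day 56. This stands. It leaves mainly deaths, withdrawals and missed visits in the group whose last scan is Cycle 4.
- **Data cut-off adds little.** For 500 and 625 mg BID (SAP 2.4), a patient first dosed on 31 December 2014 is at Day 120 on 29 April 2015, already inside the Cycle 6 window. This stands.
- **The day count matters.** A reader might infer that a Cycle 2 scan can never reach 6 weeks. That holds only in elapsed days; with +1, Day 42 qualifies. Conversely, the Day 84 anomaly in DCR exists only with +1. The two cannot be claimed together, so step 2 shows both counts.
- **A general tolerance exists.** Protocol 9.1 allows ± 1 day for procedures unless otherwise indicated. It governs when procedures are done, not how a duration is judged, and the scans have their own window. Even if applied, it would move the last on-time days only to 43 and 85.
- **DCR is descriptive.** It is secondary, carries no test, and centres are pooled. That limits the consequence but does not make the rule programmable.

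**Conclusion.** The mismatch is real, and the SD rules conflict. It affects two groups: non-responders and unconfirmed responders whose only qualifying scan is Cycle 2, and non-responders whose progression is first seen at, or whose last scan is, Cycle 4. The last-scan group should be small. ORR is unaffected.

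A reader might infer that SD and DCR are driven by scan day rather than by disease. The documents do not support that. With an 8-week minimum counted from first dose, a patient whose only SD scan is Cycle 2 fails the measurement rule on every window day. Under run-to-progression, anyone still stable at Cycle 4 and rescanned at Cycle 6 passes 12 weeks whatever the Cycle 4 day.

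A reader might also size the effect by assuming a median and counting everyone who progresses between the first two scans, or everyone without a later scan. Such figures include responders, who count towards DCR anyway, and need a rate of missing later scans that the documents do not give. No percentage of patients affected can be derived. Table 5's 27.3 points is only the share of one small Phase 1 DCR that rests on SD.

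The conclusion assumes counting from first dose, as in Appendix A's SD duration rule. It is worth correcting because, read literally, the rules can turn an on-time Cycle 2 SD into PD and can make DCR turn on one window day for some non-responders.

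**What to change.** In the SAP and Appendix A:
1. Count from first dose with the +1 convention already used for OS and PFS.
2. Replace the 6-to-8-week range with one SD minimum that includes the scan window: an SD assessment on or after Day 35.
3. Define disease control as CR, PR, or non-progression at the Cycle 4 or a later assessment (on or after Day 77), with PD at the Cycle 4 scan counted as no disease control.
4. Apply the same rules to investigator and IRR assessments.

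All 8 window days then qualify at both scans, against at most 1 of 8 now, and the Day 84 anomaly disappears. No new data are needed. The cost is that the SD count may rise slightly and DCR becomes a nominal 12-week measure that can be met from 11 weeks (77/7 = 11).
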